12.2 Secondary Objectives Analysis

Hypotheses for testing secondary objectives are formulated in the similar way as for the primary efficacy objective. If an interim analysis is performed and the trial doesn't stop, then all the subsequent secondary analysis will be tested at a reduced alpha level, i.e. what's left from the interim analysis. The confidence interval will be higher than 95% instead of 95% at the final analysis.

All secondary efficacy objectives will be evaluated based on the Efficacy FAS, but analysis for the key secondary objective will be also repeated based on Efficacy PPS. For non-key secondary objectives, if the percentage of vaccinated subject excluded from the FAS is greater than 5%, a secondary analysis based on the PPS will be performed to complement the FAS.

Similarly to the primary efficacy objectives, a Cox PH model will be used to estimate absolute vaccine efficacy VE for each secondary objective 1-4.

Criteria for evaluation : if the lower limit of the 95% two-sided confidence interval for VE estimate is greater than 40% then the secondary efficacy objectives will be demonstrated.

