8.2.2.2 Success Criteria for Secondary Efficacy Objective(s)

The key secondary objective is achieved if the lower-limit (LL) of the two-sided 95% CI of absolute vaccine efficacy estimate is > 0.4 . As for the primary efficacy objective, the CI confidence level will be adjusted to reflect adjustment of type 1 error (alpha) in case of more than one interim analysis.

Other secondary efficacy/effectiveness objectives will not be tested for success.

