8.4.3.2 Analysis of Secondary Efficacy Objective(s)

8.4.3.2.1 Statistical Hypotheses

Hypotheses for testing key secondary objective are formulated in the similar way as for the primary efficacy objective. Other secondary efficacy objectives are not associated with any hypothesis testing.

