8.4.3.2.3 Statistical Methods

Similarly to the primary efficacy objectives, the PH model will be used to estimate absolute vaccine efficacy for secondary objectives 1-4. Evaluation of the key secondary objective will be done according to the conditional testing procedure. Absolute efficacy of aQIV with respect to the culture confirmed matched influenza will be demonstrated only providing successful demonstration of the primary objective (absolute efficacy with respect to RT-PCR-confirmed influenza regardless of antigenic match). This conditioning allows testing of both primary and key secondary efficacy objectives on the same significance level alpha.

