2.2.3 Secondary Efficacy Endpoints

In addition to the primary efficacy endpoint, additional endpoints for the secondary efficacy objectives are sought, based on antigenic match of culture isolated influenza to the strains of virus contained in the seasonal vaccine.

The secondary efficacy endpoints are the time to first occurrence of culture-confirmed influenza, due to

- Influenza strains regardless of antigenic match (Secondary Efficacy Objectives 2)
- Antigenically unmatched strains of influenza virus (Secondary Efficacy Objective 3).

selected for the seasonal vaccine from Day 21 to Day 180 after vaccination or the end of the influenza season, whichever is longer.

and

- Time to first occurrence of RT-PCR-confirmed influenza due to any strain of influenza regardless of antigenic match from 7 days to 180 days after vaccination or at the end of influenza season, whichever is longer (Secondary Efficacy Objective 4).

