8.4 Multiple Comparisons and Multiplicity

The K-stage group-sequential design for efficacy introduces a multiple test problem. Therefore the familywise error rate (FWER) will be adjusted via an error-spending function ([Jennison and Turnbull 1999](#)) for each stage of the interim analyses that maintains the alpha for each interim analysis.

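### SAP 12.2 gives the secondary efficacy objectives a success rule with no primary-success condition; the protocol tests only the key secondary, and only after the primary succeeds.

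*SAP*

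**What the plan says.** **Protocol.** Section 8.2.2.2 gives the key secondary objective a success criterion (lower limit of VE above 0.4) and then closes the list: "Other secondary efficacy/effectiveness objectives will not be tested for success". Section 8.4.3.2.1 repeats the point: "Other secondary efficacy objectives are not associated with any hypothesis testing". Section 8.4.3.2.3 adds the gate, under which efficacy against culture-confirmed matched influenza "will be demonstrated only providing successful demonstration of the primary objective". It also gives the reason: "This conditioning allows testing of both primary and key secondary efficacy objectives on the same significance level alpha".

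**SAP.** Section 12.2 formulates hypotheses for the secondary objectives in general, on the pattern of the primary. It says "a Cox PH model will be used to estimate absolute vaccine efficacy VE for each secondary objective 1-4". It closes with a single criterion, that if the lower limit of the two-sided 95% interval for the "VE estimate is greater than 40% then the secondary efficacy objectives will be demonstrated". Section 12.2 separates key from non-key objectives only when it says which analyses are repeated on the per-protocol set. Section 8.4, the multiplicity section, opens with "The K-stage group-sequential design for efficacy introduces a multiple test problem" and deals only with error spending across interim looks.

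**The concern.** The two documents give different answers to a basic question: which efficacy claims may be made, and under what condition. The SAP is the document from which the analysis is programmed, and its rule has no condition attached.

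Followed as written, 12.2 permits two kinds of claim that the protocol rules out:

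- a key secondary claim when the primary has failed;
- a claim on any-strain culture-confirmed, unmatched-strain or early (from Day 7) efficacy, whatever the primary shows.

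The protocol spends no separate alpha on the key secondary. Its error control comes entirely from the gate, so leaving the gate out removes that control. If the difference is still open at unblinding, choosing between the two rules could be challenged as data-driven.

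**Working it through.** **1. The texts side by side**

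| Question | Protocol | SAP |
|---|---|---|
| Which secondary efficacy objectives have hypotheses? | Key secondary only (8.4.3.2.1) | Secondary objectives in general (12.2) |
| Which have a success rule? | Key secondary only (8.2.2.2) | Stated for the secondary efficacy objectives in the plural (12.2) |
| Must the primary succeed first? | Yes (8.4.3.2.3) | Not stated in 2.2.1, 2.4, 5, 8.4, 12.1, 12.2 or 14.1 |

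SAP 2.2.3 fixes the numbering. It labels the Day 7 endpoint "at the end of influenza season, whichever is longer (Secondary Efficacy Objective 4", and any-strain and unmatched-strain culture-confirmed influenza as objectives 2 and 3. The range 1-4 in 12.2 therefore covers the key secondary and all three others.

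**2. The plan's own power figures**

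Inputs from SAP section 5: margin VE 40% (HR 0.6), one-sided alpha 0.025, 1:1 allocation. Single-look power is Φ(√(d/4) × |ln(HR/0.6)| − z).

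- Primary, d = 238, HR 0.4: Φ(3.128 − 1.960) = 87.9%. A two-stage calculation with the boundaries in SAP 14.1, Table 1 (0.00625 and 0.35022 at 119 events, 0.02275 at 238, futility binding) gives 86.45%, against 86.5% stated.
- Key secondary, d = 144, HR 0.35: Φ(3.234 − 1.960) = 89.9%, against about 88.5% stated.

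The inputs are therefore read correctly.

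**3. Illustration of the consequence**

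The endpoints are nested, so independence figures would overstate the problem. The simulation used:

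- any-strain culture = matched + unmatched;
- primary = any-strain culture + PCR-only = 238;
- the Day 7 endpoint = primary + early cases.

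True VE is set at 40% for every endpoint, so each case falls in the aQIV arm with probability 0.6/1.6 = 0.375. With x of k cases in the aQIV arm, z = [ln 0.6 − ln(x/(k − x))] / √(1/x + 1/(k − x)), and success is z > 1.960. There is one final analysis and no interim.

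The mix is 144 matched (the SAP's figure), with 40 unmatched, 54 PCR-only and 15 early cases assumed. Counts are fixed, with 1,000,000 trials:

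| False claim | Rate |
|---|---|
| Primary | 2.3% |
| Key secondary with the primary failed | 1.3% |
| Primary or key secondary, no gate | 2.3% + 1.3% = 3.6% |
| Primary or key secondary, with gate | 2.3% |
| At least one of four secondaries, SAP rule | 5.5% |
| At least one of four, with the primary failed | 3.5% |
| Primary or any secondary, SAP rule | 5.8% |

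Under the protocol's rule the last row would be 2.3%.

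**4. Sensitivity to the assumed mix**

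The grid had 117 mixes (matched 40-165, unmatched 20-150, early 5-30), each at one-sided 0.025 and 0.02275, with counts varying randomly around the mix.

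| False claim | All VE 40% | Unmatched VE 20%, others 40% |
|---|---|---|
| Key secondary with the primary failed | 1.1-1.8% | 1.3-2.3% |
| Primary or key secondary, no gate | 3.4-4.1% | 1.8-3.4% |
| Primary or key secondary, with gate | 2.2-2.4% | 0.0-1.5% |
| At least one of four secondaries | 4.6-6.6% | 1.8-3.9% |
| At least one of four, with the primary failed | 2.6-4.8% | 1.8-2.8% |

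Holding counts fixed over the grid, with all VE at 40%, widens the ranges through discreteness: for example, 3.4-4.8% for primary or key secondary without the gate, and 4.2-7.7% for at least one of four.

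**The case against.** The strongest reply has four parts.

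- **Silence is not permission.** The SAP nowhere says that the key secondary may be claimed after a failed primary, and the protocol's gate has not been revoked. This would carry weight if 12.2 said nothing about success. It does not: it says the objectives are demonstrated if the limit exceeds 40%, without condition, and that conflicts with a rule allowing the claim only after primary success.
- **The range 1-4 belongs to the estimation sentence.** That is correct, and protocol 8.4.3.2.3 also estimates VE for objectives 1-4 without testing 2-4. But the hypothesis sentence in SAP 12.2 is general and the criterion is plural, so the wide reading is the natural one.
- **The SAP elsewhere keeps the hierarchy.** Section 2.2.1 sets out to demonstrate the key secondary, 2.2.2 only to evaluate the others, and 2.4 ties study success to the primary and key secondary. This stands, and it suggests a drafting error. Section 1 of the SAP also says that it serves protocol V5 but is based on version 4.0, so the text may have been carried over; the documents do not show which. None of these sections states the gate or narrows the 40% rule.
- **The effect is modest.** This also stands. Study success is untouched, and the rates assume VE exactly at the margin, against planned values of 60% and 65%. The case rests on the contradiction, not on the rates.

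**Conclusion.** The concern holds. SAP 12.2 conflicts with protocol 8.2.2.2 and 8.4.3.2.1 on objectives 2-4, and with 8.4.3.2.3 on the condition for the key secondary. This follows from the texts alone, within the SAP sections available for review.

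The size is illustrative. In the boundary case, losing the gate raises the chance of a false primary or key secondary claim by a little over one percentage point in the mix built on the SAP's 144 matched events. Applying the rule to all four secondaries puts the chance of at least one false secondary claim at roughly twice the nominal 2.5%. Both depend on the assumed case mix, and the second falls if unmatched-strain VE is below 40%. The primary analysis and overall study success are not affected. The correction should be made before unblinding, because the documents currently disagree on which claims are allowed.

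**What to change.** - In SAP 12.2, limit the hypothesis and the 40% criterion to the key secondary objective.
- In SAP 12.2 and 8.4, state that the key secondary is tested only if the primary succeeds, at the same adjusted alpha and confidence level as the primary at that analysis. This should replace the fixed 95% in the criterion, which disagrees with the same section's statement that the interval will be wider than 95% after an interim that does not stop the trial. The exact level depends on settling the primary's final alpha (SAP 12.1 and 14.1), which is a separate matter.
- Report objectives 2-4 as VE estimates with confidence intervals and no declaration of success.

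The cost is SAP wording only, with no change to sample size, data collection or the primary analysis. The sponsor loses no claim that the protocol allows.

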13. SAFETY ANALYSIS

The analysis of safety assessments in this study will include summaries of the following categories of safety data collected for each subject:

- Vaccine exposure.
- Solicited local and systemic adverse events.

- Medically attended AE within 30 days of first-occurrence RT-PCR confirmed ILI
- Unsolicited adverse events.
- SAEs, AE leading to withdrawal, NOCD, AESI

13.1 Analysis of Extent of Exposure

The numbers and percentages of subjects with vaccinations will be summarized overall and by vaccine group. Data will be tabulated for the All Enrolled Set.

13.1.1 Safety Completeness Analysis

Solicited adverse events

The safety completeness analysis on solicited adverse events aims to identify subjects who completed diary cards, irrespective of severity. The analysis will show the number of subjects with valid data by solicited adverse event and time point. Valid data in the context of the safety completeness analysis are all data entered in the diary card (including implausible values) except “Not done/unknown”.

Four summaries will be produced:

1. The frequencies of subjects who provide diary cards by vaccine group.
2. For each solicited adverse event, the frequencies of subjects with valid data will be presented by vaccine group and timepoint: 30 min, 6h –Day 3, Day 4-7, 6h - Day 7, Day 1 – 7 (with/without 30 mins).
3. For each type of solicited adverse event (local, systemic) and indicators of solicited adverse events, such as analgesic use, the frequencies of subjects with valid data by vaccine group, aggregated over time points: 30 min, 6h –Day 3, Day 4-7, 6h - Day 7, Day 1 – 7 (with/without 30 mins).
4. For each solicited adverse event, the frequencies of subjects with valid data by vaccine group, aggregated over time points: 30 min, 6h –Day 3, Day 4-7, 6h - Day 7, Day 1 – 7 (with/without 30 mins).
5. For the corresponding percentages, the denominator will be the respective numbers of exposed subjects, i.e., subjects who received a vaccination and were still in-study for that time point or time interval, irrespective of whether a diary card was present or not.

All analyses will be based on the ‘as treated’ Solicited Safety Set.

13.2 Solicited Local and Systemic Adverse Events

For details please refer to section 7.1.1 of the protocol.

Only solicited local and systemic adverse events reported in the diary card will be analyzed. Implausible measurements will not be taken into consideration in the analysis but listed in the Appendix (see [section 6.3](#)).

Solicited adverse events will be reported at 30 minutes, at 6 hours on Day 1 and then daily until Day 7 using structured diaries. The analyses of solicited adverse events will be done separately for 30 minutes and based on three intervals: 6h - Day 3, Day 4 - 7 and 6h - Day 7, each without 30 minutes data. In addition solicited adverse events ongoing after Day 7 will be presented as unsolicited AE.

For erythema and induration, and ecchymosis recorded originally as diameters (mm), the following categorization will be used to summarize the data:

Type I: none (0 mm), any (1-24 mm, 25-50 mm, 51-100 mm, >100 mm)

Type II: Grade 0 (< 25 mm), any (25-50 mm, 51-100 mm, >100 mm)

Body temperature will be broken down by route of measurement according to the recommendations of the Brighton collaboration as well as CBER and will be summarized according to the 3 schemes described below:

- Brighton:
 - <38.0,
 - 38.0 - 38.4
 - 38.5 - 38.9
 - 39.0 - 39.4
 - 39.5 - 39.9
 - 40.0 – 40.4
 - 40.5 – 40.9
 - $\geq 41.0^{\circ}\text{C}$
- CBER: 38.0–38.4, 38.5-38.9, 39.0-40.0, >40°C
- <38.0, $\geq 38.0^{\circ}\text{C}$

Fever, defined as a body temperature of $\geq 38^{\circ}\text{C}$ irrespective of route of measurement, will be integrated to the summaries as a systemic adverse event.

The analyses will encompass summaries of the data on five levels:

1. Daily reports of subjects with solicited adverse events.

2. Time of first onset of solicited adverse events 30 min measurement (after 30 minutes).
3. Solicited adverse events, maximum event severity by event and interval 6h - Day 3, Day 4 -7, and 6h - Day 7, each without 30 min.
4. Duration of solicited adverse events, including ongoing AE after Day 7.
5. Solicited adverse events and indicators of solicited adverse events, occurrence of at least one event by category (local, systemic) and interval 6h-Day 3, Day 4-7 and 6h-Day 7, each without 30 min.

For each of the time points or time intervals presented in the summaries, only subjects with at least one plausible observation (i.e., any non-missing values but excluding “Not done/unknown” and implausible values) for the solicited adverse events in the interval of interest will be considered. Subjects without plausible data (i.e. missing values or reported as “Not done/unknown” and implausible values) will be removed from the denominator to prevent a downward bias (towards zero).

Level 1: Daily reports of solicited adverse event

For each of the time points only subjects with at least one plausible observation (i.e., any non-missing values but excluding “Not done/unknown” and implausible values) for the solicited adverse event in the interval of interest will be considered. Subjects without plausible data (i.e. missing values or reported as “Not done/unknown” and implausible values) will be removed from the denominator in order to prevent a downward bias (towards zero). Data collected will be summarized (frequencies and percentages of subjects) by vaccine group, solicited adverse event, vaccination number and time point.

Level 2: Time of first onset of solicited adverse events

The **time of first onset** is defined, for each subject, for each solicited adverse event, as the time point at which the respective solicited adverse event first occurred. For erythema, induration, and ecchymosis the following threshold will be used: ≥ 1 mm. The summary will provide the frequencies and percentages of subjects with first onset of each solicited adverse events by vaccine group and by each time point.

The following example is used to illustrate how the onset data is selected:

Suppose four subjects, who receive vaccination A, have the following post-vaccination data for solicited adverse event XY

Table 13.2-1: Example for Time to First Onset of Solicited Adverse Events

Vaccination	Subject Number	6 Hours	Day 2	Day 3	Day 4	...	Day 7
1	001	None	Severe	Moderate	None	...	None
	002	Mild	None	None	Moderate	...	Missing
	003	Moderate	Mild	None	Severe	...	Mild
	004	Mild	Mild	None	None	...	Not done

Level 3: Solicited adverse events, maximum event severity by event and interval

The **maximum event severity** will be defined if there is at least one plausible non-missing observation (excluding “Not done/unknown” and implausible values) within this time interval, Each subject’s data will be aggregated across the time points of the interval and summarized according to the maximal severity observed for each adverse event, followed by a summary across subjects for each vaccine. Subjects without any solicited adverse events in the interval, i.e., missing values at each of the requested time points, will be removed from the denominator.

Level 4: Number of days with solicited adverse events

The number of days with the adverse event is defined irrespective of severity. This means at least ‘mild’ solicited adverse event that are assessed qualitatively and ≥ 1 mm for erythema and induration and ecchymosis. If a solicited adverse event continues beyond Day 7 the period after Day 7 is added.

The following example is used to illustrate how the duration is calculated:

Suppose six (6) subjects, who received a vaccination have the post-vaccination solicited adverse event data shown in the table below. In addition, there are unsolicited adverse event reports indicating that the adverse event in subject 003 and 006 continued until Day 12 and Day 8, respectively. For subject 003 the number of days is calculated as 6+5 and for subject 006 as 3+1. Missing values (‘Missing’) are not taken into consideration

Table 13.2-2: Example for Number of Days With Solicited Adverse Events

Subject Number	6 Hours	Day 2	Day 3	Day 4	Day 5	Day 6	Day 7	No. of days
001	None	Severe	Moderate	None	None	None	None	2
002	Mild	None	None	Moderate	Moderate	Moderate	Missing	4
003	Moderate	Mild	None	Severe	Severe	Severe	Mild ^a	11

Subject Number	6 Hours	Day 2	Day 3	Day 4	Day 5	Day 6	Day 7	No. of days
004	None	None	None	None	None	None	Not done	0
005	None	Mild	Mild	Missing	Missing	Missing	Missing	2
006	Severe	None	Mild	None	None	None	Severe ^b	4

^a continued until Day 12; ^b continued until Day 8

The frequency distribution of the number of days will be provided in a summary table by vaccine and by adverse event.

Level 5: Solicited adverse events, occurrence of at least one event by category (local, systemic) and interval.

The **occurrence of at least one solicited adverse event** is defined as “any” for a subject if he/she reports greater than “none”, ≥ 1 mm for erythema, ecchymosis and induration) for the respective event and “none” otherwise. The occurrence of at least one solicited adverse event (i.e., none versus any) will be summarized by category (i.e., local, systemic, any), by vaccine group, by vaccination (after each vaccination and after any vaccination) and by time interval.

Medications to treat or prevent pain or fever will be summarized by frequencies and percentages of subjects reporting use of the medications by interval 30 min, 6h - Day 3, Day 4 -7, and 6h - Day 7.

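### The SAP's duration summary for solicited events tabulates minimum values as exact ones when a diary stops while the reaction is still present

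*SAP*

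**What the plan says.** SAP Section 13.2 lists five levels of summary for solicited adverse events. The fourth is "Duration of solicited adverse events, including ongoing AE after Day 7". The Level 4 text has a different heading, which speaks of a number of days, but it introduces its worked example as showing how the duration is obtained.

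The rule has three parts:

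- Any severity counts: "The number of days with the adverse event is defined irrespective of severity".
- Later days are appended: "If a solicited adverse event continues beyond Day 7 the period after Day 7 is added".
- Missing diary values "are not taken into consideration".

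Three rows of Table 13.2-2 matter here. The columns are subject, 6 hours, Days 2 to 7, and the resulting number of days:

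- "001 None Severe Moderate None None None None 2"
- "002 Mild None None Moderate Moderate Moderate Missing 4"
- "005 None Mild Mild Missing Missing Missing Missing 2"

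The results go into a frequency distribution by vaccine and by event. Section 13.2 states no flag, censoring rule or separate category for incomplete diaries. Elsewhere in the same section, subjects without plausible data "will be removed from the denominator to prevent a downward bias (towards zero").

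**The concern.** Subjects 001 and 005 receive the same value for different reasons. Subject 001 recorded the event on Days 2 and 3 and then recorded its absence on Days 4 to 7. Subject 005 recorded it on Days 2 and 3 and then recorded nothing. For 001, 2 days is an observed duration. For 005 it is only the shortest duration the data allow. A reader of the final table could not tell them apart and would take both as reactions lasting 2 days.

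Solicited reactogenicity through Day 7 is a primary safety objective, and duration is one of its planned summaries. What is at stake is whether that summary describes how long reactions lasted, or only how many symptomatic days happened to be written down.

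**Working it through.** **Inputs.** The diary entries, the reported continuations (003 to Day 12, 006 to Day 8) and the stated results all come from SAP Table 13.2-2.

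**Formula implied by Level 4.** Days = (entries of Mild, Moderate or Severe from 6 hours to Day 7) + (reported days after Day 7). Missing and Not done add 0.

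**Reproducing the plan's figures, with the range the data allow.** The upper value assumes that every unrecorded day up to Day 7 had the event.

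| Subject | Recorded days with event | Days after Day 7 | SAP result | Unrecorded days | Range by Day 7 plus reported continuation | Event present at last recorded entry, later entries absent |
|---|---|---|---|---|---|---|
| 001 | 2 | 0 | 2 | 0 | 2 | no |
| 002 | 4 | 0 | 4 | 1 | 4 to 5 | yes |
| 003 | 6 | 5 | 11 | 0 | 11 | no |
| 004 | 0 | 0 | 0 | 1 | 0 to 1 | no |
| 005 | 2 | 0 | 2 | 4 | 2 to 6 | yes |
| 006 | 3 | 1 | 4 | 0 | 4 | no |

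All six stated values (2, 4, 11, 0, 2, 4) reproduce, and they do so only if unrecorded days contribute zero. Any continuation of 002 or 005 past Day 7 would come on top of the ranges shown.

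**Direction.** For any subject, true days = recorded days + unrecorded days that had the event. The second term cannot be negative, so the tabulated value is never too long and may be too short.

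**Effect on the planned table.** The example's frequency distribution is 0 days: one subject; 2 days: two; 4 days: two; 11 days: one. One of the two at 2 days (005) and one of the two at 4 days (002) are minimums. That is two of the five subjects with a reaction.

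**Is the gap closed elsewhere?** Only in part.

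- Protocol Section 3.4.2 bars later additions to the diary and requires blank fields to be recorded as missing. A solicited event described later goes to the adverse event form as unsolicited.
- SAP Section 13.2 analyses only solicited events reported in the diary, and Level 4 adds only days after Day 7. If subject 005 said at Day 22 that the reaction had lasted to Day 6, no stated rule would bring that into the duration.
- SAP Sections 8.2.1 and 13.1.1 report missingness and completeness by period, but neither is linked to the duration table.

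**The case against.** The strongest reply is that Level 4 is headed as a count of days and is correct as one. Subject 002's count spans two days without the event and 003's spans one, so the quantity is not the length of an episode. Read that way, 2 is accurate for subject 005 and only the duration label is at fault. This is right about the heading. But the SAP's list of summaries calls the quantity a duration, and so does the introduction to the example, so that is how the table will be read.

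Several stronger readings are tempting, and the documents do not support them.

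- *That the SAP declares missing days free of the event, or the reaction completed.* It says neither. The equivalence is numerical: in a count, ignoring a day and scoring it as absent give the same total.
- *That the example measures the bias.* A reader might average it: 23/6 = 3.83 days under the rule, against 28/6 = 4.67 if 002 and 005 continued to Day 7. The six subjects are invented for illustration, and the SAP plans a frequency distribution, not a mean. Subject 004 has no recorded reaction to truncate.
- *That the 5% missing-data allowance gives a study-level size.* That figure takes 1,053 selected subjects per arm to at least 1,000 evaluable. It is not a rate of diaries that stop during a reaction.
- *That the rule contradicts the SAP's denominator rule.* The denominator rule removes subjects with no plausible data in an interval. It does not address partly completed diaries, and Levels 3 and 5 also use whatever days are available. The stated aim of avoiding a downward bias applies equally well to Level 4, but there is no formal contradiction.
- *That a missing Day 7 followed by a reported continuation is handled inconsistently.* No example shows this case; 003 and 006 both have Day 7 recorded.

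It also stands that importance is limited. The solicited endpoint is the percentage of subjects with events (Protocol Section 8.1.1.1, SAP Section 2.1.4). Protocol Section 8.4.2.1.2 does not mention duration, and Protocol Section 8.2.1.1 sets no safety success criterion.

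**Conclusion.** The point holds as a minor reporting defect. A quantity presented as duration mixes exact values with minimums and does not mark which is which. Its direction is certain: the table can only understate duration. Its size in this trial is unknown, because it depends on how many diaries stop while an event is present, and the documents give no such rate, overall or by arm. For the same reason no bias between arms can be claimed. The ranges of 2 to 6 days for 005 and 4 to 5 for 002 assume that each unrecorded day up to Day 7 may or may not have had the event. Only this descriptive summary is affected; occurrence, severity and efficacy results do not use the Level 4 count.

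**What to change.** In SAP Section 13.2, Level 4, add a separate category, 'at least n days (incomplete)', tabulated by vaccine group. It should hold subjects whose last recorded diary entry shows the event, whose later entries are missing or not done, and for whom no continuation is reported. Correct Table 13.2-2 accordingly: 002 becomes ≥4 and 005 becomes ≥2. The example's distribution would then read 0 days: one; 2 days: one; at least 2 days (incomplete): one; 4 days: one; at least 4 days (incomplete): one; 11 days: one.

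Do not fill in missing days, even between symptomatic ones. Protocol Section 8.4.2.1.3 and SAP Section 8.2.1 both rule out imputation of missing solicited events. No new completeness table is needed, since SAP Section 13.1.1 already reports valid data by vaccine group and interval.

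The cost is a few lines of SAP text, one derivation and one extra category in one descriptive table. No new data are required.
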